## **5. STUDY DESIGN**

### **5.1. Development Phase**

A two cohort Phase II, open-label, non-randomized, multi-center study with 5 centres in Spain and 5 centres in Germany to evaluate the activity and tolerability of Pazopanib in patients with advanced and/or metastatic liposarcoma who have relapsed following standard therapies or for whom no standard therapy exists.

The drug will be separately investigated in the following liposarcoma subtypes (cohorts):

- Well-differentiated liposarcoma/de-differentiated liposarcoma (ALT-WD)
- Myxoid/round cell liposarcoma.

A total of 17 eligible and treated patients will be included (in each stratum) in the first step of the study. If  $\leq 3$  successes are observed in a stratum, the trial will be stopped in this stratum with the conclusion that the drug should not be further investigated in this histology. Otherwise, patients will continue to be accrued. Each cohort will independently recruit a maximum of 37 patients. The statistical analysis will be performed in each stratum.

### **5.2. Patient Screening Identification**

Informed consent should be obtained prior to start of the specified screening window. Procedures conducted as part of the subject's routine clinical management (e.g., blood count, imaging study such as bone scan) and obtained prior to signing of informed consent may be utilized for screening or baseline purposes provided these procedures are conducted as specified in the protocol. Once both clinical and biological samples informed consent forms are signed a trial screening number will be assigned to each patient. Each site will receive inside the Site Investigator File a screening log form in which pre-determined screening numbers will be assigned. This document should be always at site under Investigator staff custody. This screening number will identify patients throughout the procedures needed to confirm the subjects' suitability for the trial Protocol (clinical laboratory tests, imaging, central pathological review, etc.).

An additional document will be provided in the Investigator Site File with detailed Patient Screening Identification procedures.

### **5.3. Central pathological review**

Once a patient has signed the biological samples consent form, at least one representative formaline fixed paraffin embedded tumour block and H/E (haematoxylin/eosin) slides from all the different areas of the tumor will be collected for central pathological review. Patients may be included in the study with H/E slides only, but just if the tumor block is not available (all efforts should be done to send a representative tumor block). Representative histological sections should be sent for review in those cases without paraffin block, including H/E and other necessary stains. The diagnostic report, including macroscopic description of the specimen should be shipped together with the samples in all cases. First diagnosis sample or another more recent available sample obtained during the routine care previous to study entry will be acceptable. Tumour biopsy at study entry will NOT be

compulsory but recommended if clinically acceptable (ex. superficial or easily accessible locations). All the samples from Spain and Germany will be sent by courier to the central laboratory and diagnosis will be available in approximately one week. The central pathological review is a pre-requisite for entering the trial. The study treatment should not be initiated unless the diagnosis is confirmed by means of the central pathological review.

[figure not shown]
All the slides will be returned to the patient site with a formal report as per specific form after pathological central review. The paraffin blocks will be sent first to the translational research coordinator. All remaining samples will also be returned after the end of the project.

Central Review of diagnosis will be carried out by:

For sending the biological samples, please contact to:

A central review report will be generated as per specific form and will be replied to sites. For sending the biological samples, please contact to:

All samples will be shipped codified as is specified in the detailed tumour collection and shipment procedures.

[figure not shown]
An additional document will be provided in the Investigator Site File with detailed tumour collection and shipment procedures.

#### **5.4. Patient Inclusion**

After confirming that the patient is suitable for inclusion in this trial (inclusion/exclusion criteria), a patient trial number will be centrally assigned to each subject.

The procedure for patient inclusion is as follows:

- Complete and sign the patient inclusion forms (the patient registration forms should be signed by a clinician identified at signature list and delegation of responsibilities log.
- Please, send completed and signed patient inclusion form to:

- 
- [REDACTED] will proceed with patient inclusion procedure, and
  - Will reply site, sending the confirmation of patient inclusion form, both by fax and email. The confirmation of patient inclusion will contain the patient trial number.
  - The treatment with Pazopanib should be started **only** if site has received the confirmation of inclusion forms.

The patient trial number will identify patients throughout the participation in the study.

An additional document will be provided in the Investigator Site File with detailed Patient Inclusion procedures.

### ***5.5. Treatment description***

The treatment with Pazopanib should be started **only** if site has received the confirmation of inclusion forms as per section 5.4 of this protocol.

Pazopanib 800 mg (2x400mg or 4 x 200 mg) per day, once a day, should be taken orally without food at least one hour before or two hours after a meal until disease progression, the development of unacceptable toxicity, non-compliance, withdrawal of consent by the patient, or investigator decision.

Pazopanib should be stored in a secure area under the appropriate physical conditions for the product. Access to and administration of the investigational product will be limited to the investigator and authorized site staff. Pazopanib does not require any special storage conditions. Investigational product (Pazopanib) should begin within 7 days of inclusion (longer delays must be discussed with Study Chair).

For Pazopanib dose modifications, please, see in section 7.6 of this protocol.

Stock of Pazopanib will be centrally managed by [REDACTED], in case of any issue regarding Pazopanib, please contact to:

### ***5.6. Patient Scheduled Visits***

For more information, please, see in Table 5: Table of Assessments (section 8 of this protocol).

### **5.6.1. Before treatment:**

Informed consent must be obtained prior to start of the specified screening window. Procedures conducted as part of the subject's routine clinical management (e.g., blood count, imaging study such as bone scan) and obtained prior to signing of informed consent may be utilized for screening or baseline purposes provided these procedures are conducted as specified in the protocol.

Screening: To determine patient eligibility, within 14 days prior treatment start, it should be performed the following assessments: consent form signature, inclusion/exclusion criteria, medical history, physical exam (with Blood pressure assessment and vital and cancer signs and symptoms), ECOG, concomitant medication, clinical laboratory test, ECG, LVEF (MUGA ECO), Baseline imaging CT/MRI, tumor specimen collection, serum collection.

### **5.6.2. During treatment:**

In general, physical exam with BP, concomitant medication, clinical laboratory test and ECOG status, and adverse event collection (diarrhoea, liver toxicity, etc.), should be performed in each schedule visit.

#### First 12weeks of treatment:

Week 0 (day 1): Physical exam (with Blood pressure assessment), ECOG, concomitant medication, clinical laboratory tests, treatment control and dispensing.

Week 1 (day 8): Physical exam (with Blood pressure assessment), ECOG, concomitant medication, clinical laboratory tests and adverse events.

Week 3 (day 22): Physical exam (with Blood pressure assessment), ECOG concomitant medication, clinical laboratory tests, adverse events and serum collection at the end of 3 weeks (day 22 of treatment), treatment control and dispensing.

Week 5 (day 36): Physical exam (with Blood pressure assessment), ECOG, concomitant medication, clinical laboratory tests, adverse events, treatment control and dispensing.

Week 7 (day 50): Physical exam (with Blood pressure assessment), ECOG, concomitant medication, clinical laboratory tests, ECG, Imaging (CT scan /MRI), adverse events, treatment control and dispensing.

Week 9 (day 64): Physical exam (with Blood pressure assessment), ECOG, concomitant medication, clinical laboratory tests, adverse events and treatment control and dispensing.

Week 12 (day 85): Physical exam (with Blood pressure assessment), ECOG, concomitant medication, clinical laboratory tests, ECG, LVEF determination, Imaging (CT scan /MRI),.adverse events, treatment control and dispensing.

#### From week 12 up to the End of Treatment Visit:

Every 4 weeks thereafter: Physical exam (with Blood pressure assessment), ECOG, concomitant medication, clinical laboratory tests and adverse events. Treatment control and dispensing

Every 8 weeks thereafter: ECG and Imaging (CT scan /MRI).

LVEF determination: (MUGA/ECO) will be performed at baseline and every 12 weeks +/-2 weeks (3 months) thereafter or more frequently if clinically indicated.

Serum collection: Within 72 hours after radiological response is documented.

### **5.6.3. After End of Treatment:**

End of treatment Visit (to be performed 28 days after end of treatment): Physical exam (with Blood pressure assessment and vital and cancer signs and symptoms), clinical laboratory test, ECG, adverse events.

After discontinuation of protocol treatment in patients who have not progressed, will still be re-evaluated by imaging every 8 weeks, unless they have started a new anti-cancer therapy.

After progression disease: follow up for survival, patient status (alive/dead/lost to follow up) and new anti-cancer therapy.

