### **5.7 Response evaluation**

Informed consent must be obtained prior to start of the specified screening window. Procedures conducted as part of the subject's routine clinical management (e.g., blood count, imaging study such as bone scan) and obtained prior to signing of informed consent may be utilized for screening or baseline purposes provided these procedures are conducted as specified in the protocol.

Response evaluation will be done by means of RECIST version 1.1 criteria.

Imaging Studies: CT Scan or MRI will be used for response evaluation. Disease should be captured and target/non-target identified at baseline, CT scan or MRI as appropriate. Subsequently, imaging studies required to investigate known disease should be performed on week 7, on week 12 and every 8 weeks thereafter. Imaging methods will be employed consistently during the course of each patient's evaluation during the study. After discontinuation of protocol treatment, patients who have not progressed will still be re-evaluated every 8 weeks, unless they have started a new anti-cancer therapy.

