## TABLE Of ASSESSMENT

	Before Treatment	During Treatment											After treatment		
		Week 0	W1	W3	W5	W7	W9	W 12	Every 4 weeks (after w12)	Every 8 weeks	Every 12 weeks	28 days after end of treatment	Before PD, every 8 weeks until PD	After PD every 12 weeks	
		Day 1	Day 8	Day 22	Day 36	Day 50	Day 64	Day 85							
Informed Consent	X														
Inclusion/Exclusion Criteria	X														
Medical history	X														
Physical Exam a (with vital and cancer signs and symptoms)	X	X	X	X	X	X	X	X	X	X		X	X		
ECOG	X	X	X	X	X	X	X	X	X	X			X		
Concomitant Medication	X	X	X	X	X	X	X	X	X	X					
Clinical Laboratory Tests b,c	X	X	X	X	X	X	X	X	X	X		X			
ECG d	X					X		X		X		X			
LVEF (MUGA/ECO)	X **							X				X			
Efficacy Assessment (Imaging/MRI) *	X **					X		X		X			X		
Adverse Events			X	X	X	X	X	X	X	X		X			
Tumor specimen collection 	X														
Serum collection 	X			X											
Treatment control and dispensing		X		X	X	X	X	X	X	X					
Survival															

\*Tumor assessment should be repeated in week 7 and week 12 and every 8 weeks thereafter until documented progression for patients with CR, PR, or SD and/or for patients who have discontinued study therapy due to toxicity or reasons other than progressive disease, unless they have started a new anti-cancer therapy.

\*\*Both tumor assessment before treatment and LVEF can be done up to 28 days prior the start of the treatment.

 Tumor sample will be collected before treatment.

Serum will be collected as described:

1. Within 72 hours prior starting the treatment (basal).
2. Within 72 hours after first 3 weeks of treatment (day 22).
3. Within 72 hours after radiological response is documented.
4. Within 72 hours after progressive disease is documented.

 Monitoring of BP: A measurement of BP should be taken the day of the visit +/- 3 days.

 Hematology Profile and Chemistry Profile (including liver Function) in every visit

 Thyroid function test (T4 and TSH):basal and every 12 weeks.

 ECG: Baseline, week 7 and 12 and every 8 weeks thereafter.

Unless otherwise indicated, during treatment the marge for visits / explorations is +/- 4 days and after completion of treatment +/- 7 days

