**Table 7: Disease Assessment Scope and Schedules**

Anatomic Region & Assessment Modality	Baseline	Following First Dose
Chest, abdominal and pelvic CT or MRI	To be performed on all subjects.	To be performed on all subjects in week 7 and week 12 every 8 weeks thereafter.
Head CT or MRI	Screening with CNS imaging studies (computed tomography [CT] or magnetic resonance imaging [MRI]) is required only if clinically indicated or if the subject has a history of CNS metastases. Note: subjects with a positive scan must be excluded from the study with the exception of those subjects meeting criteria in footnote 5 	To be performed only as clinically indicated.
Bone Scan	To be performed only as clinically indicated	1) To be performed only as clinically indicated (i.e. subject is symptomatic with bone pain).

- The following information must be documented: date of assessment, diagnostic technology used for each anatomic region (e.g. chest spiral CT), description of the type and site of a lesion (e.g. liver mass).
- The same method, technique should be used to characterize each identified lesion at baseline and subsequent disease assessments.
- All the baseline disease assessments should be completed within 28 days prior to the date of inclusion in the trial.
- Disease assessments should be performed at the indicated frequency following the first dose until documented disease progression, death or upon initiating another anti-cancer treatment, whichever occurs first.
- Subjects with CNS metastases at baseline will be excluded from the study with the exception of those subjects who have previously-treated CNS metastases (surgery ± radiotherapy, radiosurgery, or gamma knife) and meet both of the following criteria: a) are asymptomatic and b) have no requirement for steroids or EIACs.

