## **10. STATISTICAL CONSIDERATIONS**

### **10.1. Study Endpoints**

#### **10.1.1. Primary Efficacy Endpoint**

The primary end-point of the study is progression free survival 12 weeks after start of therapy, measured as a binary variable. This will be based on the disease evaluation performed 12 weeks after start of treatment with central radiology review. Patients who are alive and progression free at this time will be considered as successes. Patients who have progressed or are dead at this time will be considered as failure. Patients with an unknown progression status will be considered as failure. The diagnosis of progression should be based on tumor measurements, according to the RECIST 1.1 criteria.

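### The off-treatment imaging wording does not guarantee the week-12 scan for patients who stop pazopanib early without progression, and the primary endpoint rests on that scan

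*Protocol*

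**What the plan says.** **Primary endpoint.** Protocol section 10.1.1 defines it as a binary outcome: "This will be based on the disease evaluation performed 12 weeks after start of treatment with central radiology review". It adds: "Patients with an unknown progression status will be considered as failure". SAP section 2.6 repeats the rule and extends it to status that is not available.

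**Wording that omits week 12 for patients off drug.**
- Section 5.6.3: "After discontinuation of protocol treatment in patients who have not progressed, will still be re-evaluated by imaging every 8 weeks", unless a new anti-cancer therapy has begun. No schedule precedes this sentence.
- The after-treatment part of Table 5 has an imaging column headed only by an 8-weekly interval up to progression.
- Section 5.7: "After discontinuation of protocol treatment, patients who have not progressed will still be re-evaluated every 8 weeks". Section 8.2 (item 13) and section 10.2 carry the same sentence. In all three, the paragraph first sets scans at week 7 (section 10.2: week 6/7), week 12 and every 8 weeks after that.

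**Wording that keeps week 12 for patients off drug.**
- Table 5 footnote: "Tumor assessment should be repeated in week 7 and week 12 and every 8 weeks thereafter until documented progression". It covers patients with response or stable disease and/or is meant "for patients who have discontinued study therapy due to toxicity or reasons other than progressive disease, unless they have started a new anti-cancer therapy".
- Table 7 requires chest, abdominal and pelvic imaging for all subjects at weeks 7 and 12 and then 8-weekly. Its fourth note reads: "Disease assessments should be performed at the indicated frequency following the first dose until documented disease progression, death or upon initiating another anti-cancer treatment".

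**Success in the sample size section.** Section 10.4 describes success as documented stabilisation or response once at least 12 weeks of therapy have passed. Section 10.1.1 counts the 12 weeks from the start of treatment, whether or not the drug is still being taken.

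**The concern.** Section 5.6.3 is where a site would naturally look when a patient comes off drug. It prescribes an 8-week interval and leaves open whether that interval runs from the last scan, the stop date or the first dose. Section 5.6.2 lists the week-12 scan among the on-treatment visits, which makes it easy to think that the scan lapses when the drug stops.

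Stopping before week 12 without progression is foreseeable. Section 6.3.1 lists unacceptable toxicity, non-compliance and a treatment delay of more than 3 weeks, and Tables 2 and 3 contain many discontinuation rules. A patient in this group may be progression-free at week 12 but have no week-12 scan. With unknown status scored as failure, such a patient can count against the drug because a measurement was not made. The decision in each stratum turns on 11 successes in 37 patients, so one or two such patients matter.

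**Working it through.** **Step 1: does an 8-week interval reach week 12?** The window after completion of treatment is ±7 days (note under Table 5), so a week-12 scan means weeks 11 to 13. The protocol names no start point, so each plausible one is tried for a stop before week 12:

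| Interval counted from | Next scans | Scan in weeks 11–13? |
|---|---|---|
| First dose | 8, 16 | No |
| Week-7 scan | 7 + 8 = 15 | No |
| Stop date, week s | s + 8 | Only if s = 3, 4 or 5 (weeks 11, 12, 13) |
| Baseline scan, b weeks before start (b = 0 to 4, from the 28-day allowance) | 8 − b, 16 − b | Only if b is about 3 or 4 (weeks 13, 12) |

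Example: a patient is stable at week 7 and stops in week 8. The next scan falls at week 15 (from the last scan) or week 16 (from the stop date). With the 7-day window, the earliest date in this example is week 14. Most start points miss week 12, but not all.

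**Step 2: reproduce the design.** Inputs from section 10.4: p0 = 0.20, p1 = 0.40, n1 = 17, stop at 3 or fewer, n = 37, positive at 11 or more. The exact two-stage binomial is

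P(go | p) = Σ over x = 4 to 17 of P(X1 = x) × P(X2 ≥ 11 − x), with X1 ~ Bin(17, p) and X2 ~ Bin(20, p).

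- At p = 0.20: P(go) = 0.0948 (type I error).
- At p = 0.40: P(go) = 0.9033 (power); probability of a stage-1 stop = 0.046.

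A search for the smallest expected sample size under p0 with both errors at most 10% returns this same design, so the stated figures hold.

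**Step 3: effect of lost successes.** Suppose k of 37 patients are true week-12 successes scored as failures for lack of a scan. The documents give no value for k, so it is an assumption. The rate seen is 0.40 − k/37.

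| k | Rate seen | Power | Stage-1 stop at a true 40% |
|---|---|---|---|
| 0 | 0.400 | 90.3% | 4.6% |
| 1 | 0.373 | 83.9% | 7.2% |
| 2 | 0.346 | 74.9% | 10.9% |

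One patient in 37 is 1/14.8, or about 7%, of the expected true successes (0.40 × 37 = 14.8). With a smaller loss of 2.5% of true successes, the rate is 0.40 × 0.975 = 0.39 and power is 88.2%.

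**Step 4: direction.** The mechanism turns successes into failures and never the reverse. At a true rate of 20% the probability of a positive result therefore cannot exceed 0.0948.

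**The case against.** The strongest reply is that the protocol already answers the question. The Table 5 footnote deals with patients who stop for reasons other than progression and keeps weeks 7 and 12. Table 7 says the same for all subjects from first dose, and section 5.6 sends the reader to Table 5. On this view a specific rule governs a loosely worded general one.

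Much of this stands. A reader might infer that the plan drops the week-12 scan for patients off drug, but no section says so. In 5.7, 8.2 and 10.2 the word for continuing re-evaluation can be read as carrying on the week-7 and week-12 schedule set out just before it. Some start points for the interval also land in the week-12 window.

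A reader might also infer that every patient without a week-12 scan must be a failure. That goes too far as well. Failure attaches to unknown status, and a scan at week 15 without progression shows that the patient had not progressed at week 12. The clearly indeterminate cases are those with no week-12 scan and progression at the next one. The protocol does not, however, say that a later scan may be used, and 10.1.1 points to the week-12 evaluation.

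Three further limits hold. Patients who start a new anti-cancer therapy leave scanning under every version, so they are not part of this problem. Counting unknown status as failure is prespecified and conservative. Section 10.4, read literally, could make an early stopper a failure whatever scan is done, so repairing the imaging text alone might not settle how these patients are scored.

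The reply does not remove the conflict. Section 5.6.3 has no lead-in schedule, and the after-treatment column of Table 5 disagrees with that table's own footnote.

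**Conclusion.** The inconsistency is real and touches the primary measurement. The off-treatment wording does not guarantee the week-12 scan, although other parts of the protocol require it. A site can follow 5.6.3 in good faith and leave a progression-free patient without the evaluation that 10.1.1 relies on.

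The harm is a possible loss of power and a higher chance of wrongly closing a stratum at stage 1. Its size depends on how many true successes are lost, which the documents do not give, and on 10.1.1 being applied without crediting later clean scans. The power figures are therefore illustrations of sensitivity, not forecasts. This is a should-fix: a wording conflict with a cheap remedy, acting only against the drug.

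**What to change.** 1. Align section 5.6.3, the after-treatment column of Table 5 and the off-treatment sentences in 5.7, 8.2 (item 13) and 10.2 with the Table 5 footnote and Table 7. Assessments for patients who stop without progression stay at weeks 7 and 12 counted from first dose, then every 8 weeks, until progression or new anti-cancer therapy.
2. State in Protocol 10.1.1 and SAP 2.6 that a later central scan without progression, taken before any new anti-cancer therapy, establishes progression-free status at week 12.
3. Reconcile the success wording in 10.4 (time on therapy) with that in 10.1.1 (time since start of treatment), so that early stoppers are scored by one rule.

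The cost is wording in the protocol and SAP. The week-12 scan is already planned under the Table 5 footnote and Table 7; for some patients who stop early it would take the place of a later scan.
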